7. PROJECT ASSESSMENTS

(STROBE 7; HRO Annex 2/1.2)

Project Periods	Screening				
Visit	Before T1	T1	T2	T3	T4
Time-frame in days post injury (PI)		28±12	84±14	150±18	10 day before discharge until discharge
Screening: In- /Exclusion Criteria	x				
Participant Information and Informed Consent	x				
Demographics		x			
Medical History/medication/mortality		x	x	x	x
Co-morbidities (ICD-10)					x
Questionnaires: - ISCoS core data set, pulmonary function data set and quality of life data set - questionnaire on individual respiratory muscle training, regular physical exercise and therapies		x	x	x	x
Tests: - in- and expiratory muscle strength - lung function (FVC, FEV1, PEF, PCF)		x	x	×	x

7.1 Project flow chart(s) / table of procedures and assessments

7.2 Assessments of primary endpoint/outcome

The primary endpoint of this study is the diagnostic accuracy of inspiratory muscle strength for predicting or excluding clinical pneumonia. Diagnostic accuracy of positive and negative results will be evaluated by the area under the receiver operating characteristic (ROC) curve, which provides an operational measure of the intrinsic ability of the diagnostic test by offsetting the true positive rate against the false positive rate (13). Based on our previous evidence, MIP was defined as the primary diagnostic lung parameter (14). The potential additive diagnostic value of various other lung parameters, including forced vital capacity (FVC), forced expiratory volume in 1 second (FEV₁), peak expiratory flow (PEF), peak cough flow (PCF) and maximum expiratory muscle strength (MEP) will also be investigated. The two measures for the primary endpoint, maximal inspiratory pressure (MIP) and the event of clinical pneumonia, are assessed as follows.

Inspiratory muscle strength will be measured using a hand-held respiratory pressure meter (Micro RPM, Micro Medical, Hoechberg, Germany) by an independent study nurse of each participating study site. All measurements will be performed with the patients sitting upright in their own wheelchair. Patients have to breathe through a mouthpiece while wearing a nose clip. Each measurement will be repeated three times. The greatest value of each parameter will be used for analysis (15).

For each event of pneumonia the following information will be recorded: date of event; duration of event; physician diagnosed; and type. The differentiation of the type of pneumonia is important and will be evaluated using patients medical records data following the pneumonia flow diagram of "Disease and Control Prevention / National Healthcare Safety surveillance definition of health care—associated infection and criteria for specific types of infections in the acute care setting" (16). To determine the type of pneumonia the methods x-ray, signs and symptoms and the laboratory are used. Finally four different types of pneumonia can be diagnosed.

Pneumonia 1: clinically defined pneumonia

Pneumonia 2: pneumonia with common bacterial or filamentous fungal pathogens and specific lab findings

Pneumonia 3: pneumonia with viral and other uncommon pathogens and specific lab findings Pneumonia 4: pneumonia in immunocompromised patients

Figure 1: Pneumonia flow diagram for patients of any age (16).

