Objective(s):	The main objective of this study is to evaluate 'cut-off levels' of inspiratory muscle strength as predictor for pneumonia in individuals with SCI (diagnostic accuracy). Additionally, to evaluate lifestyle and treatment parameters as well as personal- and lesion characteristics as further potential determinants of pneumonia as well as the impact of pneumonia on quality of life and mortality.
Endpoint(s):	Primary study outcome: Diagnostic accuracy of inspiratory muscle strength for prediction of pneumonia. Main secondary study outcomes: Personal- and lesion characteristics, other parameters of respiratory function, lifestyle and treatment parameters, quality of life and mortality
	due to pneumonia.

Inclusion / Exclusion	Inclusion:								
criteria:	Male and female, age ≥ 18 years, AIS A, B, C or D lesion, lesion level C1- T12								
	Exclusion:								
	Neurologic diseases (e.g. MS, ALS), 24h mechanical ventilation								
	dependency, mental disorders								
Project assessments,	Measurements:								
procedures:	- in- and expiratory muscle strength (5min)								
	- lung function (FVC, FEV ₁ , PEF, PCF) (10 min) Questionnaires:								
	- ISCoS core data-set								
	- ISCoS pulmonary function data sets								
	- ISCoS quality of life questionnaire								
	- questionnaire on individual respiratory muscle training, regular physical								
	exercise and therapies								
	- individual medication/vaccination and other medical complications will								
	be assessed from patient's medical records								
	All measurements will be performed at each measurement time-point (up								
	to 4 times during inpatient rehabilitation) and last about 40 min per patient								
	and measurement time-point in total (time with patient).								
Number of	Regarding the in- and exclusion criteria, we made a calculation of a								
Participants:	realistic numbers of subjects who can be recruited for this study per year								
	and center, based on the number of patients admitted to the								
	corresponding center during the last years								
	Estimated numbers of patients per year for each center are as follows:								
	Switzerland: SPZ Nottwil: 30 patients								
	Balgrist Zuerich: 20 patients								
	Rehab Basel: 20 patients								
	CRR Sion: 5 patients								
	Germany: BG Hamburg: 30 patients								
	Austria: Haering: 30 patients								
	Tobelbad: 30 patients								
	Australia: Heidelberg: 40 patients								

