3.2 Rationale for the research project

To determine diagnostic accuracy of our concept of using 'cut-off levels' for inspiratory muscle strength to predict pneumonia in the management of SCI, replication in a large longitudinal multi-center cohort study is essential. Only a multi-center study may allow a larger sample size and the increase in power needed for an in-depth analysis of generalizability of and variation in 'cut-off levels' across settings and patient groups.

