4. OBJECTIVES, ENPOINTS/OUTCOMES AND OTHER STUDY VARIABLES

4.1 Objectives (STROBE 3)

The primary objective of the study is to evaluate diagnostic accuracy of 'cut-off levels' for inspiratory muscle strength as predictor for pneumonia in individuals with SCI.

Specific aims include:

1) to evaluate lifestyle and treatment parameters as well as personal- and lesion characteristics as potential other determinants for pneumonia;

2) to evaluate the association between pneumonia and quality of life as well as mortality due to pneumonia.

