8. STATISTICAL METHODOLOGY

8.1 Determination of Sample Size (STROBE 10)

Regarding the in- and exclusion criteria, we made a calculation of a realistic numbers of subjects who can be recruited for this study per year and center, based on the number of patients admitted to the corresponding center during the last years.

Estimated numbers of patients per year for each center are as follows:

Switzerland:	SPZ Nottwil:	30 patients
	Balgrist Zürich:	20 patients
	Rehab Basel:	20 patients
	CRR Sion:	5 patients
Germany:	BG Hamburg:	30 patients
Austria:	Haering:	30 patients
	Tobelbad:	30 patients
Australia:	Heidelberg:	45 patients
The Netherlands:	Rijndam:	20 patients

Heliomare: 20 patients

Overall, we will be able to recruit about 250 patients per year for this study.

Overall sample size: 625 patients

With an anticipated number of 625 subjects over a 2.5 years recruitment period, we may detect about 250 cases of pneumonia (under the assumption of a 40% incidence rate (6, 7).

Moreover, taking the diagnostic accuracy (i.e., area under the curve (AUC)) of 0.86 from a retrospective study as reference (14), the envisioned sample size of at least 250 cases per diagnostic group should allow for detecting a diagnostically and clinically relevant effect (i.e., change in AUC) of 0.07 to 0.05 with 95% confidence level and 80% power (18).

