To evaluate the diagnostic accuracy of markers of lung function (particularly MIP) for predicting or excluding clinical pneumonia we will use contemporary receiver operating characteristic (ROC) analyses techniques that allow for adjusting of covariate effects (21). Such adjustments principally facilitate an unbiased estimate of pneumonia classification accuracy of potential marker(s) by controlling for the effects of other factors, such as for instance individual patient characteristics, disease traits, or site-specific features of measurement or diagnostic procedures. In case covariates affect discrimination (i.e., the ROC curve), nonparametric and parametric estimators have been proposed and implemented as to combine marker and covariate information in describing the improvement in discriminatory accuracy (21-23). Importantly, these methodologies thus also support the evaluation of adjusted ROC curves by individual patient characteristics (e.g., gender, age) or SCI characteristics (e.g., lesion level, lesion completeness, temporary or permanent artificial ventilation).

Regression modelling of secondary outcomes

Analyses of secondary outcomes will make use of common regression models, or extensions of these models. The choice of regression model will be determined by the statistical nature of the secondary outcome variable, in particular its error distribution (19). We thus anticipate using multiple regression for the modelling of the lung parameters MIP, MEP, FVC, FEV₁ and PEF, if needed using appropriate transformations as to meet normality assumptions. In case a normal error distribution is not achieved,

the outcome variable will be converted into a ordinal variable with multinomial categorical outcomes using clinically-relevant cut-offs and analysed using ordinal regression or stereotype regression, the latter in case of failure to meet proportional odds assumptions (24-26). Alternatively, a binary cut-off combined with logistic regression analysis may be used.

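### The primary objective concerns MIP cut-off levels, but the only planned accuracy measure is the AUC; no cut-off is estimated or validated

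*Combined protocol and SAP*

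**What the plan says.** Section 4.1 sets the target: "The primary objective of the study is to evaluate diagnostic accuracy of 'cut-off levels' for inspiratory muscle strength as predictor for pneumonia". The objective in the synopsis is worded to the same effect. Section 3.2 calls for replication and gives, as the reason for a multi-centre study, an "in-depth analysis of generalizability of and variation in 'cut-off levels' across settings and patient groups".

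Section 7.2 then names the measure: "Diagnostic accuracy of positive and negative results will be evaluated by the area under the receiver operating characteristic (ROC) curve". For the primary analysis, section 8.3.2 (Advanced regression modelling) plans "contemporary receiver operating characteristic (ROC) analyses techniques that allow for adjusting of covariate effects (21"), with adjusted curves by patient and injury characteristics. Section 8.1 takes an "area under the curve (AUC)) of 0.86 from a retrospective study as reference (14") and bases the sample size on a change in that AUC. The ancillary analysis section adds a non-parametric ROC approach and a comparison of imputed with complete data.

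None of these sections gives an MIP threshold, a rule for choosing one, a sensitivity, specificity or predictive value at a threshold, or any internal or external validation. The cut-offs that section 8.3.2 does mention serve to categorise secondary lung-function outcomes.

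**The concern.** A positive or negative result exists only once a threshold is set. The AUC sets none: it is the probability that a randomly chosen case has a lower MIP than a randomly chosen non-case, taken over all thresholds together. The objective therefore has no matching estimate in the analysis plan.

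Two things are at stake. The study is meant to support predicting or excluding pneumonia, which needs error rates at a usable MIP value, and two markers with the same AUC can differ widely there. In addition, if the cut-off is chosen after the curve has been seen, with no stated rule, the natural choice is the best-looking point. Its apparent accuracy is then on average too favourable, most of all in the subgroup splits foreseen in the section on datasets to be analysed.

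**Working it through.** **1. The plan's own figures.** From section 8.1: 250 per year × 2.5 years = 625 patients; 0.40 × 625 = 250 cases, hence 375 non-cases. For the AUC, use the binormal variance V(A) = 0.0099·exp(−a²/2)·(6a² + 16), with a = 1.414·z(A), equal groups, two-sided 5% (assumed) and 80% power.

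- V(0.86) ≈ 0.0925, V(0.895) ≈ 0.0717, V(0.91) ≈ 0.0617, V(0.93) ≈ 0.0473.
- One AUC against the reference, 0.86 to 0.91: n = (1.96·√0.0925 + 0.842·√0.0617)² / 0.05² ≈ 259 per group.
- Two independent AUCs, 0.86 to 0.93 (null variance taken at the mean AUC, 0.895): n = (1.96·√(2 × 0.0717) + 0.842·√(0.0925 + 0.0473))² / 0.07² ≈ 228 per group.
- At exactly 250 per group, the detectable rises are 0.051 and 0.067.

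The stated 0.05 and 0.07 are therefore reproduced, to rounding, for a rise in AUC. They say nothing about precision at a cut-off.

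**2. Does an AUC of 0.86 fix accuracy at a cut-off?** Binormal curve, r = SD in cases / SD in non-cases (assumed), b = 1/r, a = z(0.86)·√(1 + b²) with z(0.86) = 1.080. Sensitivity at 90% specificity = Φ(a − 1.282·b).

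| r | b | a | Sensitivity at 90% specificity |
|---|---|---|---|
| 0.7 | 1.429 | 1.884 | 52% |
| 1.0 | 1.000 | 1.528 | 60% |
| 1.5 | 0.667 | 1.298 | 67% |

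It does not.

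**3. Bias if the cut-off is optimised on the same data.** Simulation with an equal-variance binormal model, AUC 0.86 and one MIP value per patient. The cut-off maximises sensitivity + specificity (Youden). Optimism is the apparent minus the true value of that sum at the chosen cut-off. The model, the Youden rule and the two smaller sizes are assumptions; the documents give none of them.

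| Cases / non-cases | Mean optimism, sensitivity + specificity |
|---|---|
| 250 / 375 | about 2.6 points |
| 125 / 188 | about 3.8 points |
| 62 / 94 | about 5.8 points |

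At 250/375, apparent and true sensitivity average 0.787 and 0.771 (1.6 points). Specificity averages 0.787 and 0.778 (0.9 points). Apparent exceeds true performance in about 79% of simulated studies.

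**4. Other ways of setting the cut-off, at 250/375.** Fixed in advance: optimism −0.0003, that is, none. Read at 90% specificity or at 90% sensitivity: 0.002 to 0.003.

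**5. Ordinary sampling error, for scale.** The 95% half-width for a sensitivity of 0.78 with 250 cases is 1.96·√(0.78 × 0.22 / 250) = 0.051.

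**The case against.** The strongest reply is that an ROC curve is sensitivity against 1 − specificity at every threshold. Section 7.2 describes that trade-off, and section 8.3.2 plans whole covariate-adjusted curves and not just an area. This stands. A reader might infer that the study cannot answer its primary question, but the documents do not support that: the needed data will be collected and the curves drawn. What is missing is a cut-off, a rule for it, and estimates and validation at it.

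A reader might also infer that any cut-off read off the same curve will look better than it is. That is too broad. The bias belongs to a cut-off optimised on the data. It is an average effect, absent for a pre-fixed cut-off and almost absent for one read at a fixed specificity or sensitivity. The plan names no Youden rule, so the figures show what could happen and do not describe a stated procedure. At full size the bias is also smaller than the sampling error of about 5 points.

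The true sensitivity of the selected cut-off spans 67% to 86% (central 95% of simulations at 250/375), which might be read as optimism. It is instability: specificity moves the other way, and their true sum stays between 1.525 and 1.555 against a maximum of 1.555. It supports a CI for the cut-off, not a larger claim of bias.

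Finally, differences between settings are partly handled: adjustment for site features, random effects for clinics or countries, and subgroup analyses. That also stands, but adjusting for site takes centre differences out of the estimate. It does not show whether one cut-off performs at another centre, which section 3.2 promises.

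**Conclusion.** The point holds as a mismatch between objective and measure. Sections 3.2 and 4.1 and the synopsis ask about cut-off levels; sections 7.2, 8.1 and 8.3.2 deal in the AUC and the ROC curve, and no section estimates or validates a cut-off. This follows from the text and needs no simulation.

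The secondary risk, over-optimistic accuracy, is conditional on optimising the cut-off on the same data. Under the stated assumptions it is modest at the planned total size and roughly doubles at an assumed 62/94. The plan should be changed on this point. The data can answer the question once the analysis is specified.

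**What to change.** In section 7.2 and in section 8.3.2 (Advanced regression modelling):

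- Next to the AUC, report sensitivity, specificity, PPV and NPV with 95% CIs at an MIP cut-off. The cut-off is either carried over unchanged from the retrospective study, if that study produced one (the documents do not say), or derived by a rule stated before analysis.
- For any data-derived cut-off, use bootstrap optimism correction or leave-one-centre-out validation. Repeat the cut-off search in each resample and give a bootstrap CI for the cut-off.
- Show performance by centre descriptively and pool very small centres. Sion, at 5 per year, would give about 5 × 2.5 = 12.5 patients and 0.40 × 12.5 = 5 cases; detecting 4 of 5 has a Wilson 95% CI of 38% to 96%.
- In section 8.1, state the expected precision, about ±5 points for a sensitivity of 0.78 with 250 cases, because the sample size is justified on the AUC only.

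The cost is SAP wording and some extra computation, with no new data. Reported accuracy will be slightly less favourable where a correction applies.

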7.3 Assessment of secondary endpoint/outcome(s)

Secondary endpoints of this study include the various lung parameters mentioned above; other medical complications; quality of life; co-morbidities, medication and vaccination and mortality, in particular pneumonia-related death.

The various lung parameters thus include maximal inspiratory pressure (MIP), maximum expiratory pressure (MEP), vital capacity (FVC), forced expiratory volume in 1 second (FEV₁), and peak expiratory flow (PEF).

The peak cough flow (PCF) will be measured by having the person cough as forcefully as possible through a peak flow meter.

Medical complications will be assessed from the patient's medical records by the study nurse without involvement of the patient.

Quality of life (QoL) will be evaluated using the Quality of Life Basic Data Set of the International Spinal Cord Injury Datasets. This measurement instrument accepts (QoL) as a multi-facetted concept and includes three questions as to capture general quality of life (overall well-being), rating of physical health, and satisfaction with psychological health (17).

Co-morbidities will be assessed only once using the ICD-10 codes after the end of inpatient rehabilitation. This will also be assessed from the patient's medical records by the study nurse without involvement of the patient.

Medication and vaccination will be assessed at each measurement time-point (T1-T4) from the patient's medical records by the study nurse without involvement of the patient.

Mortality will be defined as pneumonia-related, if a prevailing event of pneumonia was clinically resolved as the initiating factor of the cascade of morbid events leading directly to death. Similarly, other causes of death will be recorded as part of all-cause mortality and as potentially competing risks of death.

7.4 Assessment of safety and reporting (HRO Art. 20. 21)

An annual safety report will be submitted once a year to the local Ethics Committee via local Investigator.

For multi-center studies the annual safety report contains information from all sites including information from sites outside of Switzerland. The Sponsor-Investigator prepares it, and then submits it to the participating Investigators. The participating Investigators submit it to the local committees.

7.4.1 Definition of Serious Events (SEs) (HRO Art. 21)

A **serious event** is any unfavourable event for which a causal relationship to sampling of biological material or the collection of health related personal data cannot be ruled out, and which:

- requires hospitalisation or prolongation of an inpatients' hospitalisation,
- · results in persistent or significant disability or incapacity, or
- is life-threatening or results in death,

If a serious event occurs the research project will be set on hold.

7.4.2 Assessment and Documentation of SEs (HRO Art. 20, 21)

The assessment will be done by the Principal Investigator with regard to the project-specific measure relation according to the following definitions:

Unrelated: The occurrence of the event has no temporal relationship to the project-specific measures applied and can be explained by the underlying disease or other factors.

Related: There is a plausible temporal relationship between the occurrence of the event and the project-specific, applied measures and cannot be explained by the underlying disease or other factors.

All SEs will be documented in the participants' file and on the SE report form. A sample form is appended to the Protocol and can be downloaded at www.swissethics.com.

7.4.3 Reporting of SEs, Safety and Protective Measures (HRO Art. 20)

The Principal Investigator will report any occurring SE to the responsible EC within 7 days (and to the FOPH in case of involved radioactive sources). She will also submit a report which evaluates the relationship between the event reported and the methods of collecting health related personal data or sampling of biological material within that project, furthermore proposals how to proceed with the project.

The Principal Investigator will notify the EC within 7 days of any immediate other safety and protective measures, which have to be taken during the conduct of the research project. In addition, the Principal Investigator will explain the circumstances, which necessitated the safety and protective measures.

All SAEs will be reported immediately and within a maximum of 24 hours to the Sponsor-Investigator of the study. The Sponsor-Investigator will re-evaluate the SAE and return the form to the site.

SAEs resulting in death will be reported to the local Ethics Committee (via local Investigator) within 7 days.

The other in the trial involved Ethics Committees will receive SAEs resulting in death in Switzerland via Sponsor-Investigator within 7 days.

8. STATISTICAL METHODOLOGY

8.1 Determination of Sample Size (STROBE 10)

Regarding the in- and exclusion criteria, we made a calculation of a realistic numbers of subjects who can be recruited for this study per year and center, based on the number of patients admitted to the corresponding center during the last years.

Estimated numbers of patients per year for each center are as follows:

Switzerland:	SPZ Nottwil:	30 patients
	Balgrist Zürich:	20 patients
	Rehab Basel:	20 patients
	CRR Sion:	5 patients
Germany:	BG Hamburg:	30 patients
Austria:	Haering:	30 patients
	Tobelbad:	30 patients
Australia:	Heidelberg:	45 patients
The Netherlands:	Rijndam:	20 patients

Heliomare: 20 patients

Overall, we will be able to recruit about 250 patients per year for this study.

Overall sample size: 625 patients

With an anticipated number of 625 subjects over a 2.5 years recruitment period, we may detect about 250 cases of pneumonia (under the assumption of a 40% incidence rate (6, 7).

Moreover, taking the diagnostic accuracy (i.e., area under the curve (AUC)) of 0.86 from a retrospective study as reference (14), the envisioned sample size of at least 250 cases per diagnostic group should allow for detecting a diagnostically and clinically relevant effect (i.e., change in AUC) of 0.07 to 0.05 with 95% confidence level and 80% power (18).

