3.1 Background

A spinal cord injury (SCI) often leads to paralysis of respiratory muscles (1), which causes a decrease in inspiratory volume and consequently limits the pre-cough volumes needed to produce an effective cough (2). The ability to cough is essential for airway clearance (3). With reduced cough capacity, the risk for pneumonia is increased (1). Pneumonia is still among the leading causes of death in the SCI population (4, 5). In acute SCI, up to 80% of patients are affected by respiratory complications (6) and in 51% of these cases pneumonia occurs (7), corresponding to a cumulative pneumonia incidence rate of about 40%. Unfortunately, predictors of pneumonia in SCI are still poorly understood (6).

To our knowledge, there are three studies on predictors of pneumonia in the SCI population (8, 9). Two of these studies concentrated on factors of injury and shock severity (9) or identified the level and completeness of injury as the fundamental clinical entity predicting pulmonary complications (8). However, both studies did not investigate potentially modifiable factors. The third study focused on potentially modifiable factors, such as lung function but did not cover respiratory muscle strength and did not define the inclusion of respiratory complications precisely (10). Therefore, to facilitate future evidence-based strategies to reduce the pneumonia risk in acute SCI, prevention targeted studies that aim to identify modifiable risk factors for pneumonia are urgently needed.

The current research proposal is targeted at specific parameters of respiratory function that are conceivably determinants of pneumonia risk as well as modifiable by respiratory muscle training (11, 12). In a recent study (accepted for Publication, Respiratory Care) we evaluated various respiratory function parameters and identified inspiratory muscle strength as a reliable discriminator between individuals with and those without pneumonia.

Although we identified inspiratory muscle strength as best parameter of respiratory function to discover individuals with SCI at risk for pneumonia, these data are based on a retrospective singlecenter data analysis without any detailed information on the type, time-point and severity of pneumonia. Also data on mortality due to pneumonia and other personal parameters that may influence the risk for pneumonia as well (e.g. smoking, exercise, mechanical ventilation dependency etc.) are missing in this analysis.

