6.3 Criteria for withdrawal / discontinuation of participants

Reasons for which a participant needs to discontinue from the project:

- withdrawal of informed consent
- non-compliance
- medical complications which do not allow measurements of this study
- death

In case of drop-out, the already recorded data will be used for further analyses. All data of drop-out patients will be anonymized after analysis.

We will report all reasons for withdrawal of the participants and compare the reasons qualitatively.

The study will not be stopped in case of futility, unless CTU Nottwil during the course of safety monitoring advices otherwise. In this case, CTU Nottwil will discuss potential stopping for futility with the study investigators group.

The final decision to terminate the study is taken by the Principal Investigator of the study.

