Likely extraneous variables (affecting either the exposure or the outcome) or confounding variables (affecting both the exposure and the outcome) comprise gender; age at start of rehabilitation; time since SCI. Further variables include smoking status (current smoker, former smoker, non-smoker), and pack-years; individual medication use and vaccination (particularly against influenza); and also influenza activity in the local community. Some variables may also induce mediating effects, which can be evidenced by targeted mediation analysis, or cause moderating effects, which can be verified by investigating interaction terms with specific predictor variables. In defining the actual modelling strategy, which particularly includes accounting for extraneous and confounding variables in the estimation of effect sizes for predictor variables, we will make use of the graphical software DAGitty (31).

Continuous variables, such as age and time since injury, may show a nonlinear relationship with the primary outcome or secondary outcomes. To formally evaluate and model nonlinear associations for these variables we will use multivariable fractional polynomial regression as well as piecewise/spline regression techniques in the modelling of survival time (27, 32).

Handling of sampling bias and attrition bias

As any observational study in a clinical setting, RESCOM may suffer from sampling bias, implying that the study population is not a random selection from the target population. Furthermore, attrition bias may occur, implying the selective dropout of study participants. Various factors may principally account for sampling bias as well as attrition bias, including the subjects' cultural background, gender, age, or socioeconomic status.

Descriptive and statistical approaches to evaluate and counteract sampling or attrition bias:

- Comparative descriptive analysis of baseline characteristics of eligible population that was initially invited to participate to the study with effective study participants. If appropriate, use of inverse probability weighting (derived from propensity scores for study participation) in weighted regression analysis
- Evaluation of selective attrition in relation to baseline characteristics. Again, inverse probability
 weighting for longitudinal studies can be used to counterweigh potential developing attrition bias in
 regression analysis.

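### Section 8.1 states the expected 250 pneumonia cases as a minimum, although its own inputs make 250 close to the most that can be expected

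*Combined protocol and SAP*

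**What the plan says.** Section 8.1 plans 625 patients over 2.5 years and says that "we may detect about 250 cases of pneumonia (under the assumption of a 40% incidence rate (6, 7"). The next paragraph takes an AUC of 0.86 from a retrospective study as reference and states that "the envisioned sample size of at least 250 cases per diagnostic group should allow for detecting a diagnostically and clinically relevant effect", namely a change in AUC of 0.07 to 0.05 with 95% confidence and 80% power.

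The 40% is explained in section 3.1: "In acute SCI, up to 80% of patients are affected by respiratory complications (6) and in 51% of these cases pneumonia occurs". Section 8.1 carries the 40% forward without the qualifier.

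Section 8.1 gives no allowance for losses. Section 8.3.2 (Advanced regression modelling) expects them: "Furthermore, attrition bias may occur, implying the selective dropout of study participants". Section 6.3 limits their effect: "In case of drop-out, the already recorded data will be used for further analyses".

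The schedule in section 7 places the first MIP measurement (T1) at day 28±12 after injury, that is, day 16 to 40. The section on descriptive analysis forms the two groups by whether a patient had any pneumonia in the study period. Section 7.2 provides that "For each event of pneumonia the following information will be recorded: date of event", but no section says whether a pneumonia before the MIP measurement is a case for the prediction AUC.

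**The concern.** The same number is first an expectation and then a minimum. *At least 250 per diagnostic group* could simply mean that the smaller of the two groups has 250 (about 250 with and 375 without pneumonia). But the smaller group is the pneumonia group, and 250 is its central estimate, built on an incidence that the plan itself derives from an upper figure.

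Two further things could lower the count, and section 8.1 mentions neither. Some patients may be lost, and some pneumonias may occur before the first MIP, since the incidence is an acute-phase figure and T1 comes between day 16 and day 40.

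This is the only power statement for the primary endpoint. The section on datasets to be analysed then justifies subgroup analyses by the relatively large sample. Section 8.1 also leaves open whether the 0.07 to 0.05 refers to one AUC against 0.86, two independent AUCs, or two markers in the same patients. Section 7.2 points towards the last of these as well: "The potential additive diagnostic value of various other lung parameters". How much reserve there is depends on which is meant.

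**Working it through.** **Inputs.** N = 625, incidence 40%, reference AUC 0.86, 95% confidence (taken as two-sided 5%) and 80% power, all from section 8.1; 80% and 51% from section 3.1. Incidences of 30% and 20% are assumptions, because the documents give no lower figure.

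**Expected count.** 625 x 0.40 = 250, leaving 375 without pneumonia. From section 3.1, 0.80 x 0.51 = 0.408, and 625 x 0.408 = 255. The plan's arithmetic is right, and 255 is the most its own inputs lead one to expect.

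**Chance of 250 or more.** Exact binomial with N = 625 and no loss:

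| Incidence | P(cases ≥ 250) |
|---|---|
| 40.8% | 67% |
| 40% | 52% |
| 38% (assumed) | 16% |
| 35% (assumed) | 0.5% |

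At 40% the central 95% range is 226 to 274 cases.

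**Detectable change: formulas.** Binormal variance of an AUC: V = 0.0099 x exp(−a²/2) x [(5a² + 8) + (a² + 8)/k] / cases, with a = 1.414 x Φ⁻¹(AUC) and k = non-cases/cases.
- One AUC against 0.86: solve d = 1.96 x √V(0.86) + 0.842 x √V(0.86 ± d).
- Two independent AUCs: solve d = 1.96 x √[2V(0.86)] + 0.842 x √[V(0.86) + V(0.86 ± d)].

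**Reproducing the plan's range (250/375, k = 1.5).** At 0.86, a = 1.528 and V = 0.000327, so the standard error is 0.0181.
- One AUC, increase: the standard error at 0.908 is 0.0150, and 1.96 x 0.0181 + 0.842 x 0.0150 = 0.048.
- Two independent AUCs, increase: the standard error at 0.929 is 0.0132, and 1.96 x √(2 x 0.000327) + 0.842 x √(0.000327 + 0.0132²) = 0.050 + 0.019 = 0.069.

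Together these match the stated 0.05 and 0.07. The 0.07 end comes from the two-AUC reading.

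**Fewer cases.** N = 625, binormal, increase/decrease:

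| Cases (incidence) | One AUC against 0.86 | Two independent AUCs | Power for an increase of 0.07, two AUCs |
|---|---|---|---|
| 250 (40%) | 0.048/0.052 | 0.069/0.073 | 81% |
| 188 (30%, assumed) | 0.053/0.058 | 0.076/0.081 | 73% |
| 125 (20%, assumed) | 0.061/0.068 | 0.088/0.095 | 57% |

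The last two rows also describe a quarter or a half of the 250 cases falling before the MIP measurement and being counted as non-cases.

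The two-AUC column puts the full case and non-case numbers behind each AUC. Two equal subgroups within the 625 would have only about 125 cases and 188 non-cases each.

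**Sensitivity to the variance formula.** Hanley-McNeil: V = [A(1−A) + (n₁−1)(Q₁−A²) + (n₀−1)(Q₂−A²)]/(n₁n₀), with Q₁ = A/(2−A) and Q₂ = 2A²/(1+A). Put into the same two equations, it gives smaller values. One AUC: 0.043/0.047 at 250 cases, 0.048/0.053 at 188 and 0.057/0.064 at 125. Two AUCs: 0.062/0.066, 0.069/0.074 and 0.083/0.089.

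**Paired AUCs.** With 250 cases, binormal and an assumed correlation of 0.3, 0.5 or 0.7, the detectable change is 0.058/0.061, 0.050/0.052 or 0.039/0.040.

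**The case against.** The best defence is that little changes. Section 8.1 states a range rather than a promise of 0.05, and its language is hedged. A chance near one half of reaching an expected count is true of almost any plan, and 249 cases would be no failure because precision changes smoothly. For one AUC against 0.86 with no loss, every value in the working stays at or below 0.07. This stands, and it is why the point concerns how 250 is described rather than the viability of the study.

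Losses are also partly answered. Recorded data of drop-outs are kept, weighting is available, multiple imputation is the main analysis, and pneumonia type is taken from medical records. A drop-out is therefore not automatically a lost case, and any loss rate would be the reviewer's assumption. A source is cited for the calculation, so the absence of a named variance formula is at most missing detail.

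A reader might infer that the study is too small or needs more patients. The documents do not support that: the stated range reproduces at 250 cases, and no document shows that the incidence will be below 40%. A reader might also infer that the plan counts pneumonias before the MIP as predicted cases. It does not say so; it is silent.

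The defence does not rescue the word *minimum*. Nor does it cover the two-AUC reading, the only one computed here that produces the 0.07 end.

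**Conclusion.** The point holds as a correction to the wording and the stated precision. On the plan's own inputs, 250 is the expected count and 255 its upper expectation, so it cannot stand as a minimum.

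The consequence is moderate. If one AUC is tested against 0.86, the stated range largely survives down to 20% incidence with no loss. If two independent AUCs are compared under the binormal variance, the 0.07 end is only just met for an increase at 250 cases and is missed for a decrease. It is missed in both directions at 188 cases. Hanley-McNeil leaves a small margin at 250 cases, and at 188 cases meets 0.07 for an increase only.

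These figures rest on two-sided 5%, 80% power, no loss and assumed incidences below 40%. The share of pneumonias before the first MIP is unknown and can only be shown as a range.

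**What to change.** Change the text of section 8.1 and, for item 3, the case definition in section 7.2. No extra patients and no new data are needed.

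1. Replace the minimum of 250 per group with: *about 250 pneumonia cases and about 375 patients without, if the 40% incidence (derived from an upper figure) holds and no patients are lost*.
2. Restate the detectable AUC change over a stated range of case counts, labelled as assumptions, for the comparison actually planned: one AUC against 0.86, two independent AUCs, or paired AUCs with an assumed correlation. Give the direction.
3. For the prediction AUC, name the index MIP among the up to four measurements (for example T1) and count as cases only pneumonias with onset after it, using the event dates already recorded. State how patients with an earlier pneumonia are handled, for example kept and classified by later events, with a sensitivity analysis that excludes them. Base the expected count in section 8.1 on that definition.

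The cost is fewer countable cases and a less favourable stated precision. Item 3 also settles part of the primary endpoint definition, so it should be agreed before the data are analysed.
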